3.5 Primary endpoint

The WHO proposed (https://www.who.int/blueprint/priority-diseases/key-action/COVID-19_Treatment_Trial_Design_Master_Protocol_synopsis_Final_18022020.pdf) a slight modification of a preexisting COVID-19 ordinal endpoint, adding an extra status relevant only to prevention trials (no disease), and adding an extra status to reflect the difference between simple invasive ventilation and invasive ventilation plus additional organ support (ECMO, CRRT, or vasopressors). In the interest of synchronization, we will collect data to allow comparison with either the WHO or NIAID version of the scale. For analysis purposes, our primary endpoint is the WHO COVID Ordinal Outcomes Scale at day 14 (with the recognition that no patients are expected to have the status of never having developed a respiratory illness). The details of the endpoint are displayed in Table 1.

Table 1. WHO COVID Ordinal Outcomes Scale *		
Patient State	Descriptor	Score
Ambulatory	No limitation of activities	1
	Limitation of activities	2
Hospitalized, mild disease	No oxygen therapy	3
	Oxygen by mask or nasal cannulae	4
Hospitalized, severe disease	Non-invasive ventilation or high-flow oxygen	5
	Invasive mechanical ventilation without other organ support	6

	Invasive mechanical ventilation with other organ support (e.g., ECLS, CRRT, vasopressors)	7
Death	Dead	8

ECLS: extracorporeal life support; CRRT: continuous renal replacement therapy
*The score for the day reflects the worst status for the given calendar day

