actually enrolled under that criterion. The ITT population thus simplifies to patients with laboratory-confirmed COVID-19. Summaries of safety outcomes will be performed in the safety population consisting of all patients who receive at least one dose of study medication. In a subgroup of the ITT population, we will compare study endpoints among patients who had not received azithromycin before randomization.

Primary Analysis. The prespecified primary analysis will compare the day 14 assessment of the 8-level COVID Ordinal Outcomes Scale between the randomized hydroxychloroquine and azithromycin groups. We will perform this analysis using a proportional odds logistic regression model (also called an ordinal regression model),² with randomized treatment group as the independent variable. Patient age, comorbidities (dichotomized as either no comorbidities or any comorbidities, with the comorbidities drawn from hypertension, COPD, and the Charlson constituent comorbidities³ (Table 1), and the baseline level of the COVID Ordinal Outcomes Scale will be included in the analysis as covariates. Due to restriction of the cohort to hospitalized patients, the baseline COVID Ordinal Outcomes Scale distribution will include only patients with levels 3 through 7. In a sensitivity analysis, we will include the total amount of pre-randomization azithromycin received as another covariate in the primary model.

Table 1. Charlson Comorbidities

Moderate/Severe Liver Disease
Cerebrovascular Disease (CVD)
Peripheral Vascular Disease (surgical)†
Renal disease
Peripheral Vascular Disease (diagnosis) †
Paralysis (Hemiplegia or Paraplegia)
Dementia

Mild liver disease
Congestive heart failure (CHF)
Chronic Obstructive Pulmonary Disease (COPD)
Diabetes with complications
Diabetes

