discharge. This approach will be used because persisting limitations are unlikely to have resolved and then recurred by 14 days. Similar single imputation rules will be devised for sensitivity analyses of secondary efficacy endpoints consistent with prior practice in the field and will be determined before the given analysis is performed to avoid bias from knowledge of outcomes.

Safety reporting

The HAHPs trial uses the adverse event reporting developed for the PROWESS-SHOCK trial.^{7,8} This approach is based on the high incidence of conditions resulting from the underlying disease that would be classified as adverse events if they occurred in healthy outpatients but are unlikely to be related to the study drug. Instead of being classified as adverse events, such events are monitored as study clinical or safety outcomes (Table 2). The exception to this rule are events which are either serious and study-related or which lead to permanent discontinuation of study drug. Those latter are reported as adverse events and are classified within the MedDRA taxonomy.

For reporting purposes, for each safety outcome or adverse event each patient will be classified as having experienced the outcome at least once (vs. never having experienced the outcome). We will separately provide counts (proportions) of safety outcomes and individual adverse events. In early interim analyses, comparisons of safety outcomes between treatment groups will be viewed as primarily descriptive. However, we will provide nominal p-values to compare adverse events and safety outcomes between groups without multiple comparison adjustment using the Chi square or Fisher exact test as appropriate to provide a crude assessment of the compatibility of observed differences between treatment groups with chance. Isolated p-values which are < 0.05 will be interpreted recognizing that 5% of such p-values will reach this threshold by chance in the absence of an actual effect of the treatment.

QTc was monitored at 24–48h after randomization as a study procedure. QTc monitoring at baseline was not mandatory but was described where it was available. We also described the change between baseline and 24–48h after randomization in QTc. These results will be summarized HAHPs SAP

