descriptively by treatment group. If the baseline QTc is available in at least 80% of participants, an analysis of covariance will be performed to compare follow-up QTc between treatment groups with adjustment for baseline QTc. Otherwise, a 2-sample t-test will be used to compare the follow-up QTc levels.

Table 2 Safety outcomes (measured daily for first five days)
Death unrelated to study drug or procedures
Seizure
Receipt of vasopressors
Atrial or ventricular arrhythmia
Cardiomyopathy
cardiac arrest
Hypoxemia requiring supplemental oxygen
ARDS
Mechanical ventilation
ECMO
Elevated LFTs
Pancreatitis
Acute kidney injury
Renal replacement therapy
Symptomatic hypoglycemia
Hematologic or coagulation events
Cytopenias
Severe dermatologic reaction

Nausea/vomiting
Visual changes
C. diff infection

Concomitant medications

The classes of concomitant medications listed in Table 3 were measured at baseline (before randomization) and through day 5 after randomization. Concomitant medications will be descriptively summarized overall and by treatment group. In addition, some patients in the hydroxychloroquine arm received azithromycin either before or in some cases after randomization. The proportion receiving azithromycin was recorded, and in exploratory summaries, safety outcomes will be displayed in that group as well as in the groups who received only azithromycin or only hydroxychloroquine.

Table 3. Concomitant medications
ACE inhibitors
ARBs
NSAIDs
Glucocorticoids
Immune-suppression
Chloroquine
Hydroxychloroquine
Azithromycin
Zinc
Vitamin C

Interim Monitoring.

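### SAP Table 2 safety outcomes are counted as ever versus never without requiring new onset, so states already present at entry dilute the between-arm comparison

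*SAP*

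**What the plan says.** The counting rule in SAP, Safety reporting, is that for every safety outcome or adverse event "each patient will be classified as having experienced the outcome at least once (vs. never having experienced the outcome". The outcomes and their window are given under "Table 2 Safety outcomes (measured daily for first five days". The list includes "Hypoxemia requiring supplemental oxygen", "Mechanical ventilation" and "Receipt of vasopressors", together with ARDS, ECMO and renal replacement therapy. Proportions are compared between arms in the safety population (everyone with at least one dose) by chi-square or Fisher tests, with nominal p-values and no multiplicity adjustment.

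On entry severity, SAP, Primary Analysis, states that "the baseline COVID Ordinal Outcomes Scale distribution will include only patients with levels 3 through 7". Protocol 3.5, Table 1, defines level 4 as "Oxygen by mask or nasal cannulae" and level 7 as "Invasive mechanical ventilation with other organ support (e.g., ECLS, CRRT, vasopressors". Level 6 is invasive ventilation without other organ support.

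The SAP plans to use baseline values for one safety measure only, QTc: change from baseline, and covariance adjustment if enough baseline values exist.

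**The concern.** A patient who enters on oxygen and is still on it when the first daily record is made is a hypoxemia case whatever the study drug does. The same holds for a patient who enters ventilated or on vasopressors. Such patients add equal expected counts to both arms and carry no information about treatment, yet they remain in the numerator and denominator of the comparison.

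This matters because the SAP takes these conditions out of adverse-event reporting unless they are serious and study-related or lead to permanent discontinuation of study drug. For most of them Table 2 is therefore the main between-arm safety display. Under Protocol Appendix 4 the DSMB also reviews adverse events and clinical outcomes at interim analyses. A diluted row with similar percentages in the two arms can be read as reassurance when it mainly reflects how sick patients were on arrival.

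**Working it through.** The documents give no expected rate, power or sample size for the safety comparison, so there is no stated figure to reproduce. SAP Table 4 sizes the primary outcome only.

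**Inputs from the documents.** Ever-versus-never rule and five-day window (SAP, Safety reporting and Table 2); entry at levels 3 to 7 (SAP, Primary Analysis); target of 300 patients (SAP, Sample size and power); 0.05 as the nominal threshold.

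**Assumptions.** The allocation ratio is not stated; 1:1 with all patients dosed gives 150 per arm. Baseline prevalence b and new-onset risk p are not given, so b is varied and p is set at 10% versus 20%. A patient in the state at entry is taken to be still in it on the first day measured. The test is two-sided.

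**Step 1: the diluted rate.** With b equal in both arms in expectation,

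ever-rate = b + (1 − b)p

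risk difference = (1 − b)(p₂ − p₁)

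The difference among patients at risk is thus multiplied by exactly (1 − b).

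**Step 2: power.** Normal approximation for two proportions, n per arm, D = difference, m = mean of the two rates:

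power = Φ{[D − 1.96·√(2m(1 − m)/n)] / √([p₁(1 − p₁) + p₂(1 − p₂)]/n)}

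Worked case, b = 0.5:

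- As written: rates 0.55 and 0.60, n = 150. The null standard error is √(2 × 0.575 × 0.425/150) = 0.0571 and the alternative standard error is 0.0570. (0.05 − 1.96 × 0.0571)/0.0570 = −1.09, so power is 0.139.
- New onset among patients at risk: rates 0.10 and 0.20, n = 75. The standard errors are 0.0583 and 0.0577. (0.10 − 1.96 × 0.0583)/0.0577 = −0.25, so power is 0.402.

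| b | Ever-rates as written | Risk difference | Risk ratio | Power as written | At risk per arm | Power, new onset (risk ratio 2.00) |
|---|---|---|---|---|---|---|
| 0 | 10.0% vs 20.0% | 0.10 | 2.00 | 0.681 | 150 | 0.681 |
| 0.1 | 19.0% vs 28.0% | 0.09 | 1.47 | 0.451 | 135 | 0.635 |
| 0.3 | 37.0% vs 44.0% | 0.07 | 1.19 | 0.234 | 105 | 0.528 |
| 0.5 | 55.0% vs 60.0% | 0.05 | 1.09 | 0.139 | 75 | 0.402 |
| 0.7 | 73.0% vs 76.0% | 0.03 | 1.04 | 0.086 | 45 | 0.262 |

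**Step 3: cross-check.** A chi-square simulation with 20,000 runs per setting gives power of 0.240 vs 0.540 at b = 0.3, 0.146 vs 0.399 at b = 0.5, and 0.092 vs 0.267 at b = 0.7 (as written vs new onset).

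**Step 4: no true effect.** With 10% new onset in both arms, the as-written rule rejects in 0.047 to 0.058 of runs over b = 0, 0.3, 0.5 and 0.7. The new-onset rule rejects in 0.047 to 0.052. This is expected: without an effect the ever-rate is the same in both arms, so the test is an ordinary two-sample comparison.

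**Step 5: other effect sizes.** At b = 0.5, new onset of 10% vs 25% gives power of 0.260 as written and 0.680 among patients at risk; 20% vs 40% gives 0.438 and 0.766.

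**Which rows.** On the scale, oxygen corresponds to level 4 and above, invasive ventilation to 6 and above, and additional organ support to 7. Whatever the baseline distribution, b for oxygen is at least as large as b for invasive ventilation, which is at least as large as the share at level 7. Among these rows oxygen is therefore diluted most.

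**The case against.** The strongest reply is that a state merely continuing from entry is not an event. Protocol 7.1 treats the exempt items as adverse events collected by another route and ties evaluation to the period after the first dose. Protocol A4.3 words the respiratory and vasoactive items as changes. The case report form, which the documents do not show, may record only new events. This supports the view that the protocol's authors had change in mind. It does not settle the count. Those passages govern adverse-event reporting, and SAP Table 2 lists bare states without carrying the wording over. An after-first-dose limit would not help either, since a continuing state is also present after the first dose.

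Three limits on the consequences stand:

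- The day-14 and day-7 ordinal models, the ventilator- and ICU-free days, and the daily tables of all eight levels from day 0 partly capture the same deterioration.
- The SAP calls the p-values nominal and crude, and states no decision rule that uses them.
- Renal replacement at entry should be uncommon, because Protocol 4.3 excludes chronic hemodialysis and very low GFR.

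A reader might go further and infer that chance imbalance in baseline severity will produce false safety signals, or that a real excess of respiratory or circulatory failure would be hidden from the trial altogether. The documents support neither. Chance imbalance is already within the nominal 5%, as Step 4 shows, and the analyses just listed give other views of the same deterioration.

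**Conclusion.** The point holds as a matter of dilution and lost power in those Table 2 rows that can be present at entry. The risk difference shrinks by (1 − b); this follows from the written rule, given that baseline states persist to the first daily record. The size in practice is unknown because b is not in the documents. Under the illustrative 10% vs 20%, power as written is about 71% of the new-onset figure at b = 0.1 (0.451/0.635), 44% at b = 0.3 (0.234/0.528) and 35% at b = 0.5 (0.139/0.402). Even the better count has limited power at high prevalence.

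There is no directional bias and no type I error inflation. Rows that cannot be present at entry, such as death, are unaffected, and so is the primary efficacy analysis. The change should be made, but it does not threaten the trial's main conclusion.

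**What to change.** In SAP, Safety reporting, for every Table 2 row that can be present at entry:

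- Add a count of new onset after randomization, with patients free of that specific condition before randomization as the denominator.
- Identify baseline oxygen by ordinal level 4 and above, and invasive ventilation by level 6 and above. State whether the ventilation row includes non-invasive ventilation, since level 5 pools that with high-flow oxygen.
- For vasopressors, renal replacement and ECMO, take item-specific status from the baseline CRF or the medical record. Level 7 pools them, so using it would drop a patient on CRRT from the vasopressor denominator, and it misses vasopressors given without ventilation.
- Take baseline status before randomization. Protocol Table 1 scores the worst status of the calendar day, and day 0 is the day of enrollment, so a day-0 score could class same-day deterioration after randomization as baseline.
- Show the number with the condition at baseline by arm, and keep the all-patient ever-versus-never count as a descriptive column.

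The cost is SAP wording, a baseline filter, and a check that the baseline CRF or record holds the item-specific status; no new patient procedures are needed. The downside is that denominators are smaller and differ by row. Worsening among patients already on support is not counted in the new-onset rows and must be read from the daily ordinal-scale tables. The change should be dated before treatment groups are unblinded.

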5.0 Study Procedures

Note that given the high contagiousness of SARS-CoV-2, the limited supply of personal protective equipment, and risk to coordinators' health, study visits, procedures, and monitoring will be performed in a no-touch mode. This also applies to the consenting process, which will be performed via a consenting mechanism that confirms the identity of the patient, provides access to the consent form, and obtains a signature to complete documentation, without requiring physical proximity of research staff and the study subject.

5.1 Study commencement. After informed consent and enrollment, coordinators will complete the baseline CRF, and initiate study procedures, including randomization (variable permuted block randomization by hospital).

5.2 Study drug. This is an open label, randomized, active comparator trial. Patients who are discharged home will not continue treatment after hospital discharge. If the patient has already received azithromycin or hydroxychloroquine prior to randomization (no more than 2 days), the prior doses will count toward the 5-day total dose. For enrolled patients whose laboratory testing returns negative for SARS-CoV-2, if the clinical team believes that another cause of the patient's presentation is more likely than COVID-19 in light of the negative laboratory testing, the clinical team may stop study drug. Such discontinuation will be recorded. Since the fundamental clinical question is whether to start treatment in patients with suspected or confirmed COVID-19, these patients will remain in the primary analytic cohort.

The trial will be temporarily suspended for enrollment at a given site in the event that no study drug is available at that site.

5.2.1. Hydroxychloroquine. Patients in the hydroxychloroquine arm will receive hydroxychloroquine 400mg po BID x 1 day, then 200mg po BID x 4 days³ (dose reductions for weight < 45kg or GFR<50ml/min). For patients < 45kg, doses will be halved. For patients with GFR<50ml/min, the final dose of hydroxychloroquine will not be administered. The drug dose chosen falls at the lower end of doses proposed in various international trials, but it has proven in vitro efficacy, with a ratio of lung tissue trough concentrations to the EC50 (effective concentration to suppress 50% of viral activity) of >20.³ Given in vitro confirmation of the adequacy of the dose and likely superior safety profile at the lower dose, we chose the total dose of 2.4gm over 5 days.

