Note: if the clinical attending physician believes that bacterial pneumonia is likely and requires a second antibacterial agent for "atypical" infection (an uncommon occurrence in COVID-19), patients may receive another agent (e.g., doxycycline or levofloxacin) as appropriate at the clinician's discretion.

5.2.2. Azithromycin. Patients in the azithromycin arm will receive azithromycin 500mg on day 1 plus 250mg daily on days 2-5 (may be administered IV per clinician preference).

5.3 Study Assessments. Coordinators and/or data queries will classify the COVID Ordinal Outcomes Scale on days 1–7, 14. They will also review for adverse events, including especially rash, self-report of visual changes, or symptomatic hypoglycemia. They will ensure that an EKG is performed at 24 to 48 hours post-randomization time. If a clinical EKG is not performed during this timeframe, a research EKG will be performed. In addition, ventilator status and ICU and hospital stay (using the last-off method) will be used to determine ventilator- and ICU-free days at 28 days using the worst rank ordinal technique, whereby death is scored as -1 days. In addition, coordinators and/or data queries will classify the COVID Ordinal Outcomes Scale on day 14. If this cannot be determined from the medical record, the patient will be contacted via telephone, mail, or electronic methods to determine their status on day 14.

5.2.4 Six-month assessment. A brief visit will ascertain the EQ-5D-5L to measure quality of life. Mortality and readmissions will also be assessed at that visit, which may be performed by telephone, electronic means, or in-person, depending on the subject's needs and preferences.

5.4 Approach to potential risks. Hydroxychloroquine has been used in many thousands of patients as an anti-malarial agent and in systemic lupus erythematosus and rheumatoid arthritis as a mild anti-inflammatory agent. The safety has been well established. Azithromycin has been used in millions of patients and is effective against the causes of bacterial pneumonia. Its immunomodulatory effects are also of interest in a variety of syndromes. While both agents have known side effects, such side effects are generally rare and well-tolerated.

This pragmatic study protocol is designed to optimally protect patients against risk through careful choice of exclusion criteria, pragmatic monitoring for common adverse events, and careful oversight by a DSMB.

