5.4.1 Potential risks and risk mitigation. The package insert for hydroxychloroquine lists visual impairment, cardiac impairment, QTc prolongation, worsening of psoriasis or porphyria, proximal myoneuropathy, suicidality, and hypoglycemia. Other reported risks include nausea, diarrhea, vomiting, abdominal pain, headache, dizziness, allergic reactions, rash, low blood counts, seizures, and death. All of these risks are quite rare and where observed are seen after prolonged administration, generally in the range of years. While ocular examinations are recommended after a year (and for acute symptoms), routine ocular examinations have never been recommended for brief duration of therapy. While QTc prolongation has been described, it is generally modest, and routine EKG monitoring is not normally practiced with administration of hydroxychloroquine. In addition, there is some concern that in patients with very low body weight or with low GFR the risk of adverse events may be increased. The potential risks of azithromycin primarily relate to QTc prolongation and *Clostridioides difficile* infection (CDI). Both are clearly described but quite rare with azithromycin.¹⁹ Additional risks include nausea, diarrhea, vomiting, and abdominal pain, allergic reactions, rash, infusion site reaction when given through a vein, abnormal liver function, drug interactions, development of drug-resistant bacteria, heart problems, muscle weakness, cardiac arrest, death. When hydroxychloroquine and azithromycin are co-administered, a modest prolongation in QTc may be observed, which is why we chose the more conservative threshold of 500msec rather than 550msec as an exclusion criterion.

In order to mitigate these risks, we have defined eligibility criteria that exclude patients with elevated risk, keep dosage low, and restrict treatment to just 5 days and avoid outpatient therapy. Patients are monitored within the hospital during treatment. Research coordinators and/or data queries will monitor for adverse events.

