The present research aims to investigate patients with COVID-19. Due to the nature of the condition, many of these patients will have impaired decision-making capabilities. Moreover, those with intact decision-making capacities likely have milder disease than those with impaired capacity, creating substantial risk of sampling bias. Therefore, this study could not be conducted if limited to enrolling only those subjects with retained decision-making capacity. Hence, subjects recruited for this trial are not being unfairly burdened with involvement in this research simply because they are easily available. They are the core group of patients most likely to experience benefit from hydroxychloroquine or azithromycin.

6.5 Informed consent.

Federal regulations at 21 CFR 50.20 and 45 CFR 46.111(a)(5) require that informed consent be sought from each prospective subject or the subject’s LAR. Each study participant or LAR must sign and date an IRB-approved informed consent form. The consent form (via a HIPAA authorization) will also indicate that protected health information (PHI) may be released to relevant study personnel and regulatory agencies.

Some of the patients approached for participation in this research protocol will be decisionally impaired due to their critical illness. Hence, some patients will not be able to provide informed consent. Accordingly, informed consent will be sought from the participant’s LAR, as defined at 45 CFR 46.102(c): “an individual or judicial or other body authorized under applicable law to consent on behalf of a prospective subject to the subject’s participation in the procedures(s) involved in the research.” In this study, LARs will be identified as stipulated by relevant regulations and statutes, as per the standards defined for clinical decision making, as is the standard practice in human subjects research.

According to a previous President’s Bioethics Committee (National Bioethics Advisory Committee (NBAC)), an investigator should accept a relative or friend of the potential subject who is recognized as an LAR for purposes of clinical decision making under the law of the state where the research takes place.²⁹ Finally, OHRP has stated in their determination letters that a surrogate could serve as a LAR for research decision

making if such an individual is authorized under applicable state law to provide consent for the “procedures” involved in the research study.³⁰

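### Visual changes are found by self-report, but the SAP's two-class rule counts dosed patients who could not be asked on any of days 1–5 as never having had the event

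*SAP*

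**What the plan says.** - **Classification.** SAP, Safety reporting, on how these rows are tabulated: "each patient will be classified as having experienced the outcome at least once (vs. never having experienced the outcome". There is no third class.
- **Denominator.** SAP, Analysis Sets: safety summaries use all patients who received at least one dose.
- **Window and rows.** The SAP heading reads "Table 2 Safety outcomes (measured daily for first five days". The list includes "Visual changes", symptomatic hypoglycemia and nausea/vomiting. It also includes mechanical ventilation, ARDS, vasopressors, ECMO and death unrelated to study drug or procedures.
- **How events are found.** Protocol 5.3: "They will also review for adverse events, including especially rash, self-report of visual changes, or symptomatic hypoglycemia". Protocol 5.4.1 adds: "Research coordinators and/or data queries will monitor for adverse events". Section 5.0 says that "study visits, procedures, and monitoring will be performed in a no-touch mode".
- **Who is enrolled.** SAP, Primary Analysis: baseline ordinal levels 3 through 7. Levels 6 and 7 are invasive ventilation (protocol Table 1).
- **Missing data.** SAP, Missing Data: the rules cover the primary and secondary efficacy outcomes. Nothing is said about safety outcomes that could not be assessed.
- **Comparison.** SAP, Safety reporting: nominal, unadjusted chi-square or Fisher exact p-values between arms.

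**The concern.** A patient who is sedated and ventilated for the whole window, or who dies early, cannot self-report a visual change. Under the SAP such a patient has no recorded event and stays in the denominator, so is tabulated with those who were asked and said no. The reader of the table cannot tell the two apart.

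Visual impairment is a package-insert risk of hydroxychloroquine (protocol 5.4.1), and protocol 5.3 picks out visual changes for specific review. Impaired vision is also among the events generally exempt from adverse event reporting (protocol Appendix 4, A4.3), so SAP Table 2 is the main place where non-serious cases would appear. At stake are the accuracy of that row and the reading of its between-arm comparison. The primary analysis is not affected.

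**Working it through.** The plan gives no expected rate of visual changes and no share of patients unable to report, so there is no stated figure to reproduce. The check takes assumed ranges.

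**Inputs**
- p = true rate in the window: 5%, 10% or 20% (assumed).
- u = share of dosed patients unable to report throughout days 1–5: 5% to 30% (assumed).
- 150 patients per arm: the target of 300 with 1:1 allocation, which is assumed because the ratio is not stated.

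**1. Understatement.** Reported rate = p(1 − u). At p = 10%:
- u = 10%: 0.10 × 0.90 = 9.0%
- u = 20%: 0.10 × 0.80 = 8.0%
- u = 30%: 0.10 × 0.70 = 7.0%

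In patients, p = 5% and u = 20% gives 150 × 0.05 = 7.5 true cases per arm and 7.5 × 0.80 = 6.0 reported.

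**2. Between-arm ratio when the true rates are equal.** Ratio = (1 − u_B)/(1 − u_A), whatever p is:
- equal u: 1.00
- 5% vs 15%: 0.85/0.95 = 0.895
- 10% vs 20%: 0.80/0.90 = 0.889
- 10% vs 30%: 0.70/0.90 = 0.778

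**3. Chance of a nominal p < 0.05 in that direction.** With reported rates a and b, the chance is about Φ(|a − b|/SE − 1.96), where SE = √{[a(1 − a) + b(1 − b)]/150}. With no distortion it is about 2.5%. At p = 10%:
- 5% vs 15%: 9.5% vs 8.5%, chance about 5%
- 10% vs 20%: 9.0% vs 8.0%, chance about 5%
- 10% vs 30%: 9.0% vs 7.0%, chance about 9% (16% if p = 20%)

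**4. Masking of a real excess.** Suppose the arm with more patients unable to report truly has 15% against 10%, a ratio of 1.50. Power on the true rates is about 26%.
- 5% vs 15%: 12.75%/9.5% = 1.34, power about 14%
- 10% vs 20%: 12.0%/9.0% = 1.33, power about 13%
- 10% vs 30%: 10.5%/9.0% = 1.17, power about 6%

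**5. Rough scale from the plan's own scenarios.** The planning distributions put 20.0% (Scenario 2), 28.75% (Scenario 3) and 37.5% (Scenario 1) of the azithromycin arm in levels 6–8 at day 14. At an odds ratio of 0.55 the hydroxychloroquine shares are 12.1%, 18.2% and 24.8%; for Scenario 2, odds 0.25 × 0.55 = 0.1375 and 0.1375/1.1375 = 0.121. Using these as u, the azithromycin-to-hydroxychloroquine ratios are 0.800/0.879 = 0.91, 0.7125/0.818 = 0.87 and 0.625/0.752 = 0.83. These are day-14 shares under the effect the trial was sized for, so they probably overstate the share unable to report throughout days 1–5.

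**6. Effect of an assessable denominator.** The rate becomes p(1 − u)/(1 − u) = p in each arm, and the false ratio returns to 1.00, provided that being assessable is unrelated to the risk of the event.

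**The case against.** A reader might infer that all three symptom rows are hidden in ventilated patients and that the arm with more ventilation would look better tolerated. The documents do not support that reading.

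- **Scope.** Self-report is attached to visual changes only. Symptomatic hypoglycemia is a separate item in protocol 5.3 with no stated source; chart or glucose records are possible, since monitoring may use data queries. No method is given for nausea/vomiting, and vomiting can be observed.
- **Overall tolerability.** SAP Table 2 also shows ventilation, ARDS, vasopressors, ECMO and unrelated death by arm. An arm with more of these would look worse there. At 150 per arm, a 10% vs 30% split in u is itself a z of about 4.3 (0.20/√(2 × 0.2 × 0.8/150)), so its cause would be visible.
- **Direction.** Patients ventilated at entry are balanced in expectation by randomization, so a systematic difference must arise within five days. No daily symptom review after discharge is described. Patients sent home before day 5 may also go unasked, which pulls the other way.
- **Size.** The class is at least once, so a patient who reports before intubation is captured and u is an upper limit. Protocol 5.4.1 calls the listed risks quite rare, so the absolute loss may be well below the 10% illustration.
- **Consequence.** The p-values are described as crude, and no decision rule rests on this row. Events that are serious and study-related, or that lead to permanent discontinuation, are reported separately.
- **Evidence.** No sentence says that patients who cannot report are counted as never. And where protocol 6.4 says "many of these patients will have impaired decision-making capabilities", the subject is consent, not symptom reporting.

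All of this stands and limits the point. It does not remove it: two classes, an all-dosed denominator and no rule for patients who could not be asked leave the default class as the only place for them.

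**Conclusion.** The point holds for visual changes, and for any other Table 2 row that proves to rest on patient report alone. The reported rate is understated by up to the share unable to report: on a true 10%, one to three percentage points for shares of 10% to 30%. The ratio for the row is distorted only if that share differs by arm, by about 11% for a ten-point difference (ratio about 0.89), and which arm gains cannot be said in advance. Both the shares and the event rates are assumptions; the documents give neither. That such patients end up as never is an inference from the two-class rule, though hard to avoid. This is a modest gap in safety reporting, worth closing because the data to close it already exist. It is not evidence that the safety comparison as a whole favours the worse arm.

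**What to change.** In SAP, Safety reporting, state for each Table 2 item how it is found. For visual changes, and any other item found only by patient report, keep the all-dosed count and show beside it, by arm:

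- **(a)** the number not assessable, meaning no day in days 1–5 on which the patient was alive, in hospital and at ordinal level 3–5. A patient who did report an event counts as assessable, so the numerator stays inside the denominator.
- **(b)** the rate among assessable patients.

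Do not add a rule that counts charted hypoglycemia without symptoms only at levels 6–7. It would widen the definition for ventilated patients alone and count events in people outside the denominator.

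The cost is a few lines of SAP text and one derived variable; daily scores for days 1–7 are already collected (protocol 5.3 and Appendix 1). There are limits. Assessability is determined after randomization. The level is only a proxy for ability to report, and the score is the worst status of the calendar day. A patient discharged early still counts as assessable after a single qualifying day, so later unasked days are not corrected. The assessable rate should therefore be a supplementary display.
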